# Primary end-point:

• Percentage of patients with treatment failure at day 7 after randomisation. Treatment failure is defined as either failure to administer allocated treatment for any reason or the presence of diarrhoea on day 7 after randomisation (as assessed by personnel blinded to treatment allocation).

22.9.2021 Protocol version 9.2

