## Study subjects:

- Inclusion Criteria: All of the following: Informed consent (see below), Age > 18 yrs., In-patient in ICU or HDU (incl. burn unit) and expected to stay for >7 days, Diarrhoea following antibiotic treatment defined as 3 or more stools per day or Bristol type 7 stool in the volume >300 ml/day if stool derivative device is in place, persisting for 24 hours despite enteral feeding formula has been stopped.
- Exclusion criteria: Death appears imminent or ceilings of care put in place, presence of new-onset sepsis defined as per 2016 definition, lactate >2.0 mM, colon diameter > 9 cm on plain AXR, the necessity of ongoing antibiotic treatment for another reasons. Unable to tolerate enema for any reason (e.g. surgery of the GI tract in the past year). Pregnant and lactating woman. Patients with a history of severe anaphylactic food allergy, any other reason

22.9.2021 Protocol version 9.2

which — as per judgement of the treating clinician — makes faecal transplantation unsafe or not feasible (Note: All screening failures based on this criterion will be reported separately, inc. the reason why it was considered unsafe or not feasible to proceed).

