# Intervention group :

- if considered safe, the patient receive Loperamide 2 mg p.o. 2 hours before FBT.
- FBT procedure 350 ml of thawed donor stool (stool suspension) will be delivered by retention enema in the patients colon. The patient will be positioned in left semilateral Trendelenburg's position for 15 minutes and then in right semilateral Trendelenburg's position for another 15 minutes. Faecal management system (e.g. FlexiSeal©) will be inserted and clamped for 2hours after FBT
- in all patients receiving FBT will be recorded body temperature, heart rate, oxygen saturation and blood pressure. 3hours after FBT blood culture will be taken.

- in the subset of patients with C. dif. positivity, 1 L normal saline enema will be performed at the time of CDI diagnosis and FBT will be repeated once more. No antibiotics will be administered (with rescue option of administration of i.v. tigecycline).

**FBT stool suspension** will be stored in specific –80°C freezer with connected alarm notification to guarantee continuous registration of the storage. Information on the FBT suspension labels includes donor code, suspension number, production and expiration date, volume, and storage temperature instruction. From each donor one of the sample will be store in freezer for the duration of the ongoing study.

The resulting faecal bacteriotherapy (FBT) preparation is defined as a mixture of 7 aliquots of processed stool intermediates from 7 donors.

The resulting graft will be drawn into four sterile 100 ml syringes and transferred to the ward where the recipient is hospitalized. Re-freezing of thawed or partially thawed extract is not permitted.

# Day 2, 3

Physical examination, SOFA score, evaluation of laboratory blood results (WBC, CRP, lactate, etc.) will be recorded as well as volume or frequency and consistency (Bristol scale) of stool. Concomitant medication and adverse events will be recorded.

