# Assessment of primary outcome:

An independent data analyst will retrospectively review the de-identified printouts of nursing notes from the two 12 hour shift day + night ending in the morning of day 7 and record the presence or absence of diarrhoea (defined as 3 or more stools per day or Bristol type 7 stool in the volume >300 ml/day if stool derivative device is inserted).

In case the patient is not on ICU, but remains at hospital, the research nurse will bring a special record form on day 6 and instruct both the patient and nursing staff to record during the next 24 hours the volume or frequency and consistency of stool using visual Bristol Scale and also to provide a sample of stool. In case the patient has been discharged, he/she will be contacted the day before over the phone by a research nurse and the next day the patient will be asked to bring the formulary and a stool sample to hospital of will be visited by a research staff at home.

Afterwards, as long as the patient remains on ICU, adverse events, antibiotic treatment, and stool volume/frequency are monitored daily.

Unique Protocol ID: 2021-002290-25 22.9.2021 Protocol version 9.2

In patients with faecal management device in place, follow up visits (identical to Day 4) are performed in 7 days interval up to day 28, and/or ICU discharge or FMD removal, whichever occurs earlier.

In patients who remain in ICU, but have had FMD removed, have the same follow up procedures, with the exception of stool sampling. Stool is collected and stored as close as practical to the day of the visit after the patient has had spontaneously defecated.

In patients who are not on ICU, but remain at hospital, will be visited by a research nurse at day 7, 14, 21 and 28 as long as they remain hospitalised. The visit will include monitoring of adverse event, notice on patient general status, the presence/absence of diarrhoea, antibiotic medication. Blood will be collected and frozen. Six month follow up is performed at follow up clinics and it includes history (incl. recent history of diarrhoea), physical exam and blood sampling. Patients willing to do so are requested to bring in a stool sample. Patients unwilling to show up will be interviewed over the phone.

	D0	D1	D2	D3	D4	D 5-6	D7	D14, 21, 28or D/C	6month follow up
ICF	х								
Review drug chart	Х								
Serum sample + freeze	х	x			х		x	x	х
Stool sample + freeze	х				х		х	(x)	х
Adverse events, Phys.exam, SOFA	х	х	х	х	х	х	х	х	
Blood culture		хх							

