# Monitoring of safety:

Although it is potentially beneficial and has been safely performed in ICU patients, there are only limited data about FBT safety in patients with potentially disrupted intestinal barrier. In turn, following measures have been taken to maximise safety of the current study for patients:

- Treating clinician will not be blinded to treatment allocation and they will be encouraged to speak up should any safety concerns arise.
- Before and 3 hours after FMT, vital signs, blood cultures, endotoxin and early cytokine levels will be measures to specifically look at potential bacterial translocation.
- All patients' vital functions will be continually monitored as per local standards. Frequency, volume and character (as per Bristol scale) of stools will be recorded in 12 hour intervals.
- Onset of sepsis or elevation lactate > 2mM or the presence of pyrexia >38 C with >30% rise of inflammatory markers without clear alternative reason (e.g. HAP) will trigger, in both groups, the addition of intravenous tigecycline or intravenous vancomycine, if C. dif positivity is known or suspected.
- I.v. antibiotics efficient against C. dif. can be added in both groups if a treating clinician considers this appropriate. Reason for doing so will be recorded.
- Should a SUSAR appear, it will be reported as per local legislature and within 48 hours reviewed by the team of investigators, together with independent safety advisors (prof. [name]. Dept. of Infectious Diseases, Na Bulovce Hospital, Prague and Dr.[name], REB Chair FNKV Univ. Hospital), a representative of nursing staff independent on the study. Two SUSARs in the intervention group would automatically lead to termination of the trial for safety reasons.

Unique Protocol ID: 2021-002290-25 22.9.2021 Protocol version 9.2

In addition, the same team will meet ad hoc whenever safety concerns arise. The
team will review data collected from first 8 subjects who have been randomised and
focus on the analysis of adverse events. In particular, the team will review the dynamics of body temperature, heart rate, blood pressure, lactate and blood cultures
before and after FMT. The decision will be taken to continue or terminate the study.

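### The stool-count limb of the diarrhoea definition sets no consistency, so a recovered patient without a stool device who passes three formed stools is scored a day-7 treatment failure

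*Combined protocol and SAP*

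**What the plan says.** The Primary end-point section counts as treatment failure either non-delivery of the allocated treatment or "the presence of diarrhoea on day 7 after randomisation", judged by staff blinded to allocation. The working definition of diarrhoea is in Assessment of primary outcome, where an independent analyst reads de-identified nursing notes covering two 12-hour shifts and applies this rule: "defined as 3 or more stools per day or Bristol type 7 stool in the volume >300 ml/day if stool derivative device is inserted".

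The inclusion criteria under Study subjects use the same two limbs: "3 or more stools per day or Bristol type 7 stool in the volume >300 ml/day if stool derivative device is in place". They add that the state must follow antibiotic treatment and be "persisting for 24 hours despite enteral feeding formula has been stopped".

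Stool consistency is collected in several places:
- On ICU study days: "volume or frequency and consistency (Bristol scale) of stool" (Day 2, 3, under Intervention group).
- On the form for patients who have left ICU but remain in hospital: "the volume or frequency and consistency of stool using visual Bristol Scale" (Assessment of primary outcome).
- In safety monitoring: "Frequency, volume and character (as per Bristol scale) of stools will be recorded in 12 hour intervals" (Monitoring of safety).

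None of these sections sets a Bristol cut-off for patients without a device.

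**The concern.** In both definitions the Bristol type stands with the volume threshold and the device condition. The other limb is a bare count. The analyst does not see the patient and has only the written rule. Followed literally, it gives the same result, failure, for three formed stools and for three watery ones. An analyst who adds a consistency requirement from clinical common sense is scoring an endpoint that the protocol does not contain, and two analysts could differ on the same notes.

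The primary endpoint's specificity is at stake. Recovered patients scored as failures pull both success rates down in proportion and so shrink a true difference between arms. With 36 patients there is little room for avoidable misclassification.

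**Working it through.** **1. The wording.**

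| Limb | Entry (Study subjects) | Day 7 (Assessment of primary outcome) |
|---|---|---|
| Count | at least 3 per day; no consistency | at least 3 per day; no consistency |
| Device | Bristol 7, over 300 ml/day | Bristol 7, over 300 ml/day |
| Further conditions | after antibiotics; 24 h persistence off enteral feed | none |

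The extra entry conditions concern cause and duration. Neither sets a consistency, and neither applies on day 7.

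**2. The plan's own figure.** Inputs from Sample study size: success 45% (control) and 66% (FBT), margin 20 points, one-sided 5% alpha, 80% power, 1:1 allocation.

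n per arm = (1.645 + 0.842)² × [0.45×0.55 + 0.66×0.34] / (0.20 + 0.21)² = 6.18 × 0.4719 / 0.1681 = 17.4, rounded up to 18. The total is 36, as stated.

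Power at 18 per arm: SE = √(0.4719/18) = 0.1619; 0.41/0.1619 − 1.645 = 0.887; Φ(0.887) = 81.3%.

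**3. Who can be misclassified on day 7.** Only patients who have recovered and have no device. At the planned rates the recovered number 18×0.45 = 8.1 (control) and 18×0.66 = 11.9 (FBT). Some may still have a device, so these are upper limits.

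**4. Size under an assumption.** Let m be the share of recovered patients scored as failures because of formed stools, equal in both arms. The documents give no value; 5-15% is assumed. Success rates become 0.45(1−m) and 0.66(1−m), and the difference becomes 21(1−m) points. Power is recomputed as in step 2.

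| m | Misclassified, control / FBT | Success, control / FBT | Difference | Power, 18 per arm |
|---|---|---|---|---|
| 0 | 0 / 0 | 45.0% / 66.0% | 21.0 | 81.3% |
| 5% | 0.4 / 0.6 | 42.8% / 62.7% | 20.0 | 79.0% |
| 10% | 0.8 / 1.2 | 40.5% / 59.4% | 18.9 | 76.8% |
| 15% | 1.2 / 1.8 | 38.3% / 56.1% | 17.9 | 74.8% |

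**5. Direction if FBT were truly worse.** Take FBT worse by exactly the margin, 45% against 25%. With m = 10% the rates are 40.5% and 22.5%, a gap of 18 points. SE = √[(0.405×0.595 + 0.225×0.775)/18] = 0.1519, and Φ((0.20 − 0.18)/0.1519 − 1.645) = Φ(−1.513) = 6.5%. With m = 15% the gap is 17 points, SE is 0.1497, and Φ(−1.445) = 7.4%. The nominal false-positive rate is 5.0%.

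**The case against.** The strongest reply is that everyone involved knows diarrhoea means loose stool, that the rule is identical at entry and on day 7, and that it is applied blind to both arms in a pilot feasibility trial. That limits the size of the problem. It does not remove it, because the person scoring works from printouts and a written rule that does not mention consistency. If type 7 was meant to govern both limbs, the text should say so; that reading would also leave three type 6 stools uncounted.

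A reader might infer four stronger things that the documents do not support.

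- **That two misclassified patients use up over half the margin.** Two of 18 is 11.1 points in one arm's failure rate. The 20-point margin applies to the difference between arms, and nothing in the documents puts all the error in one arm. Under equal misclassification the difference moves by about 1-3 points.
- **That the dilution biases towards non-inferiority.** Under the plan's own assumption that FBT is better, it lowers the chance of showing non-inferiority (step 4). It helps a non-inferiority claim only if FBT is truly worse (step 5). The Statistical plan section also describes an unadjusted hazard ratio with a 95% interval and no margin test.
- **That enrolment on formed stools is a comparable problem.** The wording permits it, but clinicians would have to regard formed stools, persisting a day after feeding stopped, as diarrhoea following antibiotics. That is unlikely.
- **That the arms are scored on different limbs.** The FBT procedure includes inserting a faecal management system, and no such step is listed for controls. The documents do not say how many devices remain on day 7, so unequal misclassification is possible but cannot be shown.

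One practical objection stands. Safety monitoring promises stool character in 12-hour intervals, so a Bristol type for each individual stool in the ICU notes is not guaranteed.

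**Conclusion.** The point holds as a defect in the written primary-outcome definition: the count limb can score a recovered patient as a failure, and no other section corrects it. It bears mainly on day 7 and only on recovered patients without a device who have three or more stools.

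The likely effect is modest: at most one or two patients per arm over the range tabulated above, with a loss of about 2 to 6 points of power. These figures rest on the assumed 5-15%, on equal misclassification in both arms, on the plan's success rates, and on a normal approximation. The true frequency cannot be derived from the documents and could be close to zero. The sample size of 36 reproduces and is not called into question by this point. The definition should be tightened because doing so is easy and protects the main endpoint, not because a large bias has been shown.

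**What to change.** In both Study subjects and Assessment of primary outcome, restrict the count limb to loose or liquid stools by a single Bristol cut-off. The sponsor should choose it, reconcile it with the type 7 in the device limb, and apply it identically at entry and on day 7.

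Instruct the analyst to score from the consistency already recorded in the notes or on the ward form. State a default in advance for any stool or 12-hour record without a Bristol type, for example to count it as loose. Report the unrestricted count as a sensitivity analysis, and give the number of patients whose classification changes.

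The cost is a phrase in two sections and a line in the scoring instructions, with no new assessments and no change to the sample size. The small downside is that some ICU stools may lack an individual Bristol type and will fall to the default; if it is to count them as loose, the present rule persists for those stools.

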The aim of the basic blood test is to confirm the patient's good clinical condition. The aim of other tests is to prevent the transmission of latent infection from the donor to the recipient. This complete examination of the donor is repeated after 2 months. If the following examination is also found to be physiological (ie without signs of the donor's infectious disease), the stool donated by the donor during these 2 quarantine months (frozen in the stool bank) will be considered non-infectious and can be used for the FBT method. Despite this quarantine measure, the donor is obliged to fill in a questionnaire focusing on the risks of infectious diseases during each delivery of stool. In case of a new occurrence of infectious manifestations (especially diarrhea) travelled abroad or taken antibiotics the stool donor is obliged to inform about this attending physician.

22.9.2021 Protocol version 9.2

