## Direct access to source data/documents:

Whole FBT procedure must be properly recorded in accordance with the rules on medical records and the documentation must be store for 10 years. The patient documentation shall include the performance indication, performance record, informed consent to FBT and information obtained during subsequent visits. The documentation must be kept to allow for an additional assessment of possible early and late side effects of the method. Furthermore, it will be recorded from what 7 donors the extract was used for each individual patient.

Donor documentation includes the results of clinical and laboratory testing, a completed and signed questionnaire confirming the absence of exclusion criteria and informed consent to the use faeces for medical purposes. For each frozen faecal extract, the date of freezing and, where appropriate, the place of preservation must be indicated in addition to the donor identification.

The examiner and the medical facility will allow for clinical trial monitoring, audits, oversight of the ethics committee, inspection authorities inspection and access to source documents.

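### Outside ICU, planned adverse-event collection stops at hospital discharge or day 28 and is not provided for at the six-month contact, so later harms are not systematically asked about or counted

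*Combined protocol and SAP*

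**What the plan says.** All in the combined protocol and SAP:

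- **Follow-up (Assessment of primary outcome).** On ICU, adverse events are monitored daily for as long as the stay lasts. Patients elsewhere in the hospital "will be visited by a research nurse at day 7, 14, 21 and 28 as long as they remain hospitalised", and adverse events are named among the items of those visits.
- **Six months (same section).** "Six month follow up is performed at follow up clinics and it includes history (incl. recent history of diarrhoea), physical exam and blood sampling". Stool is optional: "Patients willing to do so are requested to bring in a stool sample". The fallback is "Patients unwilling to show up will be interviewed over the phone", with no content given for the call.
- **Schedule table (same section).** The row "Adverse events, Phys.exam, SOFA" is marked from day 0 to the column for days 14, 21, 28 or discharge, and is blank at six months. The serum and stool rows are marked at six months.
- **Secondary end-points.** The adverse-event end-point is a composite number. SOFA and recurrence are given time points; this end-point is not.
- **Selection of donors.** Part of the donor testing is meant to "prevent the transmission of latent infection from the donor to the recipient".
- **Direct access to source data/documents.** Records are kept "to allow for an additional assessment of possible early and late side effects of the method".
- **Monitoring of safety.** "Two SUSARs in the intervention group would automatically lead to termination of the trial for safety reasons". No end date is given for reporting such events.

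**The concern.** Safety is a stated aim in the Abstract and under Sample study size, and Monitoring of safety says that data on FBT in patients with a possibly damaged gut barrier are limited. Each recipient receives material pooled from seven donors. The plan thus recognises possible donor-derived and late harm, yet names adverse events only for contacts during the hospital stay.

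Two things are at stake. First, a readmission with sepsis, or a new infection after discharge, would enter the safety data only if someone happened to raise it and someone else chose to record it as an adverse event. The trial is open-label, so such unprompted reporting may differ between arms.

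Second, the period over which events are counted ends, for ward patients, at a date set after randomisation. The Background says that non-clostridial diarrhoea often lengthens stay. If FBT shortened hospital stay, FBT patients would be watched for less time and could show fewer events for that reason alone.

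**Working it through.** **1. The plan's own figures.** The plan gives no figure for the adverse-event window. Its total of 36 patients reproduces with cure rates of 45% and 66%, a margin of 20 points, one-sided 5% and 80% power: n per arm = (1.645 + 0.842)² × (0.45×0.55 + 0.66×0.34) / (0.21 + 0.20)² = 6.18 × 0.4719 / 0.1681 = 17.4, rounded up to 18, so 36 in all. The present point uses this only for the 18 FBT patients in step 5.

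**2. Where adverse events are planned to be collected.**

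| Setting | Adverse events named in the text? | Stated end |
|---|---|---|
| ICU | Yes, daily | End of ICU stay; no day limit |
| Ward | Yes, days 7, 14, 21, 28 | Discharge or day 28 |
| Discharged, before month 6 | No; the only contact described is the day-7 stool assessment | – |
| Six-month visit | No | – |
| Six-month telephone interview | Content not stated | – |

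The ward visit and the six-month visit are described close together in one paragraph. One names adverse events and the other does not.

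**3. The schedule table.** The blank six-month cell points the same way, but it is weak evidence alone. Its row also covers the physical examination, which the text requires at six months. Table and text therefore conflict in this row whatever was intended. The finding rests on the text.

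**4. Length of planned collection outside ICU.** Taking six months as about 183 days, a patient who has left ICU by day 28 has at most 28/183 = 15% of participation covered, leaving 183 − 28 = 155 days. A patient discharged on day 9 (hypothetical; the plan gives no discharge times) would have 9/183 = 5%. Under an equal daily event rate, the expected count is proportional to days observed. If average observation were 21 days with FBT and 28 days in the control arm (assumed, for scale), the ratio of expected counts would be 21/28 = 0.75 with no difference in harm.

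**5. How much a late question could reveal.** The documents give no rate for late events, so a range is assumed. With 18 FBT patients, the chance of at least one late event is 1 − (1 − p)^18: 17% at p = 1%, 60% at p = 5% and 85% at p = 10%. If all 18 were asked and none reported an event, the one-sided 95% upper limit would be 1 − 0.05^(1/18) = 15% of patients. Asking makes the count interpretable; it cannot show that late harm is rare.

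**The case against.** The strongest reply is that late harm has several ways into the record. The six-month history names diarrhoea as one item and is not limited to it. An examination and blood sampling accompany it. Information from later visits belongs in the patient record, which is kept so that late effects can be assessed, and the seven donors used for each patient are recorded. SUSAR review has no cut-off, the safety team can meet whenever a concern arises, and the Ethics section requires serious side effects of FBT to be reported to the ethics committee, again without an end date.

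This stands against stronger readings that a reader might infer:

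- *Late harm would go unrecorded.* Not supported: the routes above could pick it up.
- *Late events cannot reach the two-SUSAR rule.* Not supported: nothing in Monitoring of safety excludes a post-discharge SUSAR.
- *No patient is monitored beyond day 28.* Not supported: daily ICU monitoring has no day limit.
- *The window falls short of the plan's own two-month latency.* Not supported: the two months is the interval for retesting the donor before held stool is released. The plan does not say when a transmitted infection would appear in a recipient, so the two periods should not be compared.

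What the reply does not supply is a prompt. All these routes need someone to learn of the event first. Nothing requires the six-month history or call to cover readmissions or infections, to record them as adverse events or to pass them to the safety team. No infection testing of the six-month samples is specified. Donor traceability helps only once an event in a recipient is known.

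**Conclusion.** The point holds as a gap in systematic collection. For patients outside ICU, planned adverse-event collection ends at hospital discharge or day 28, and neither the text nor the table provides for it at the six-month visit or call. The adverse-event end-point has no time window, so the time over which it is observed depends on discharge date.

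For patients off ICU by day 28, planned collection covers at most 15% of a six-month participation of about 183 days. Whether this would bias the comparison depends on discharge times and on any effect of FBT on stay, neither of which the documents give. Whether a late event would be missed depends on a rate that they do not give either. The matter is a cheap improvement to the safety data; it does not invalidate the design.

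**What to change.** 1. **Six-month contact.** In Assessment of primary outcome, state that at the visit, or the telephone interview that replaces it, serious adverse events, hospital readmissions and new infections since the last contact are recorded with dates, using the same set questions in both arms.
2. **Safety review.** State that these reports are forwarded to the safety team for assessment under the existing procedures in Monitoring of safety. Leave the SUSAR termination rule as it is; serious adverse events as such should not be added to it.
3. **Schedule table.** Reconcile the row that combines adverse events, physical examination and SOFA with the text, most simply by splitting it so that each item has its own marks, with adverse events marked at six months.
4. **End-point.** Give the adverse-event end-point in Secondary end-points a fixed window from randomisation, the same in both arms and independent of discharge. The dates from item 1 allow events to be placed inside or outside it.

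The cost is a few questions at a contact already planned in both arms, a table correction and one case report form page, with no new visit or procedure. The drawback is recall over up to six months, which will favour serious events such as readmissions over minor ones. That is still better than no planned question.
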